4.0 Research Design and Methods

4.1 Type of Study

This is a single-site study that will take place at VA Pittsburgh Healthcare System, Pittsburgh, PA. It is a prospective randomized clinical trial evaluating the two different nerve block injection drugs for TKA and THA, introduced above and described further below. All described RegA techniques strategically avoid GETA and high-dose opioids, and the immediate postoperative complications (from GETA and high-dose opioids) that inhibit full-capacity cognitive function needed to accomplish PT/OT goals during the first 2 days after TKA/THA. Two hundred (200) total patients will be recruited and evaluated for study outcomes pre-TKA/THA (100 for TKA, 100 for THA). Following pre-surgical evaluation, patients will be block-randomized (stratified by [a] TKA vs. THA surgical procedure, [b] age, and [c] presence of diabetes). After surgery, all patients will undergo the same standardized PT/OT best-evidence care plans consistent with current clinical care at our institution. Evaluation of study outcomes will take place during the first two days after surgery, throughout the remainder of the hospital stay (which typically ranges from 2 to 5 days, including discharge day), and during the first two orthopedic post-op follow-up evaluations. The primary outcome is pain at 24 hr after surgery, and exploratory outcomes include physical therapy progress and anesthesia-related symptoms. We will also assess additional metrics of anesthesia and physical therapy success such as range of motion, physical function and performance testing, length of hospital stay, discharge placement, readmission, falls, and other adverse events.

Study Treatment Groups:

Institutional Standard of Care (ISOC)

All patients will receive a standardized bupivacaine spinal anesthetic, consistent with current institutional practice. All patients will receive pre-medications for the prevention of pain, nausea, vomiting, and gastroesophageal reflux, consistent with current institutional practice. All patients will receive intravenous hydration, intravenous antiemetics, and intravenous blood pressure support (e.g., intravenous phenylephrine bolus/infusion) consistent with our current institutional practice. The need for intraoperative blood transfusion will occur based on current institutional practice and collaborative decision-making between the surgical and anesthesia teams, consistent with current institutional practice.

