If a patient has a significant health status change after the baseline visit, but before the scheduled surgery, the study team will evaluate the patient's current medical status and determine if the health status change will affect the baseline data. In the rare occasion that the study team determines the patient's baseline data will be affected, the patient will be asked to come back to the clinic for a second baseline visit. The patient will be compensated for this visit and all baseline procedures will be repeated. As this repeated baseline visit is for data integrity only, and not for safety purposes, if the patient refuses to come back in for the repeat baseline visit, they will not be removed from the study. The study team will document this as a minor protocol deviation and the patient will continue on the study as previously planned. .

Prior to the day of surgery, the patient will complete a standard of care IMPACT visit. (IMPACT: VAPHS preoperative clinic – Interdisciplinary Medical Perioperative Assessment Consultation and Treatment).

Day of Surgery

On the day of surgery, the patient will receive anesthesia/study drug. Research questionnaires will be completed pre- and post-surgical procedure. Please refer to Appendix 1 for additional details.

In-Hospital Post-op Days (1-5)

Post-op in hospital visits will occur while the patient is in the hospital.

Follow-up visits 1 and 2

These two visits will be done in conjunction with the patient's standard of care orthopedic post-op visits.

Study Procedures:

Study Questionnaires:

Short-Form McGill Pain Questionnaire (SF-MPQ) – version 2 (Specific Aim)

The SF-MPQ questionnaire will be used to measure the subject's knee or hip pain. The questionnaire consists of 15 different qualities of pain and related symptoms, in which the subject is asked to rate the intensity of each symptom on a scale (none, mild, moderate, or severe). The questionnaire also includes two additional items relating to the patient's current pain. This questionnaire takes 5-10 minutes to complete.

SF-8 Survey

The SF-8 Health Survey is a short 8-question survey designed to measure the patient's overall health at 24-hour intervals. It takes less than 3 minutes to complete (21).

Short-Form 36 Health Survey (SF-36)

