For patient-reported outcome of function, we will use the data generated by Western Ontario and McMaster Universities Osteoarthritis Index Physical Function Subscale (WOMAC-PF). The entire WOMAC instrument will be administered. This instrument was developed based on patient input and is the instrument of choice to assess outcome post-TKA and THA (20). The WOMAC-PF consists of 17 items related to physical function. Each item is scored on a 5-point Likert-type Scale with descriptors from 0-4 (none, mild, moderate, severe, and extreme difficulty). Scores of each item are summed for a maximum total score on the WOMAC-PF of 68. Higher scores indicate worse functional limitations. Reliability and validity of this instrument have been established (25-27). This will be given before surgery and at Follow-Up Visit 2 after surgery. Licensing rights to this questionnaire have been purchased by the study team for use in this research study.

Falls Questionnaire:

Throughout the study, the patients will be asked about their falls history. The information collected will include but is not limited to, how many falls the patient experienced in the past year (done at baseline), how many falls since the last assessment (in-hospital visits and Follow-Up Visit 2), questions regarding loss of balance, whether or not the patient is afraid of falling, and was medical treatment sought after any falls.

Clinical Assessments

None of the clinical assessments listed below are being done due to safety concerns, as such, if the physical therapist or treating physician feels that due to the patients' medical condition (such as a knee immobilizer), that some or all of the physical therapy tests cannot be completed at the specified protocol time points; the physical therapy testing will be considered optional for these patients and will be done at the discretion of the treating physician and physical therapist. If physical therapy testing is not completed due to the patient preparing for discharge and/or the patient has been discharged, this will not be considered a protocol deviation.

Gait Speed: Self-selected gait speed is measured in meters/second while subjects walk a 4 meter path located in the middle of a longer path of 9 meters to avoid acceleration or deceleration. Subjects are asked to walk at their regular pace, and time is measured with a stop watch. This test takes around 2 minutes.

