The tester uses a stopwatch to measure the amount of time the participant is able to stand on one limb. Time commences when the participant raises the foot off the floor. Time ends when the participant either: (1) uses the raised foot (moved it toward or away from the standing limb or touched the floor), (2) moves the weight-bearing foot to maintain his balance (ie, rotated foot on the ground), (3) a maximum of 45 seconds elapses. Three trials are performed in each side and recorded. This exam takes around 6 minutes.

Crude Sensory Examination: Sensory examination is carried out by touching lightly the patient in the specified anatomic distribution of L2-L4 and L4-S3 bilaterally, while the patient has his eyes closed. The patient is asked if the sensation is of equal intensity on both sides (normal), or if one side feels less than the other, or is unable to be felt (diminished or absent). This exam takes around 2 minutes.

Hip, Knee and Ankle Range of Motion: Range of joint movement is measured with a standard goniometer during passive (movement assisted by the tester) and active (without assistance by the tester) movements. Range of motion is tested with the subject lying in supine on the hospital bed or examination table. This is performed on both sides and recorded in degrees. Range of motion takes approximately 5 minutes.

Straight Leg Raise: The subject is asked to raise one lower extremity from the hospital bed up to approximately 45 degrees from the horizontal without bending the knee. The test is performed in both sides, and is recorded as “Yes” if the subject is able to raise the lower extremity higher than 20 degrees from the horizontal, or “No” if unable to lift the leg at that level. During this test the examiner also observes the presence of a knee extension lag, which is defined as a knee flexion (lag) equal or greater than 5 degrees during the straight leg raise. It takes approximately 3 minutes for the straight leg raise activity.

Stair climbing time: This test measures the time the subject takes to go up a flight of stairs. Subjects are instructed to use the handrail for safety purposes. The tester uses a stop watch to record time. It takes approximately 5 minutes for this test.

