Prolonged numbness in the distribution of the nerve blocks If a patient encounters numbness and weakness for an extended period of time after a nerve block is given, then certainly serious consideration is given to the possibility of nerve damage from surgery, nerve block, other factors, or a combination of these. We do not have any preliminary data indicating the duration of numbness as a separate entity from the duration of analgesia. In our preliminary data (published), the analgesic duration (with or without numbness) upper bound of the 95% confidence interval is 49 hr. By definition, the 95% interval (30-49 hr) is the interval representing that we are confident that the mean lies within this interval 95% of the time. So with the conservative 48 or 49 hr “upper bound” as the possible mean, and with a standard deviation of analgesic duration being 14 hr, we will apply a “mean and standard deviation” principle of “nerve damage” possibility. If the mean is 48 hr, and the standard deviation is 14 hr, then 97.5% of these nerve blocks’ numbness will dissipate by 76 hr (i.e., mean plus 2 standard deviations). For simplicity, if any patient has numbness (i.e., both analgesia and numbness, but not analgesia without numbness), beyond 72-76 hr after injection, then the participant will be referred (presumably while still in the hospital) to the Physical Medicine and Rehabilitation Service for initial evaluation, with subsequent referral to neurosurgery if deemed appropriate based on electromyography (EMG), imaging, or other workup. If minor symptoms of paresthesiae with pain and/or weakness persist over time, patients will be similarly referred to the Physical Medicine and Rehabilitation Service for outpatient workup, and these events will be recorded in study logs.

ISOC MMPNA Nerve Blocks From July 1, 2011 until December 31, 2014, there were a total of 1830 patient-block encounters involving our ISOC MMPNA program, entailing the routine use of 3-4 drugs in peripheral nerve blocks. At our institution, the incidence of EMG-documented nerve damage

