9.2 Recording/Reporting requirements

Eliciting adverse event information

Research subjects will be routinely questioned about adverse events throughout their hospital stay and at study visits.

Recording requirements

All observed or volunteered adverse events (serious or non-serious) and abnormal test findings, regardless of study group or suspected causal relationship to the study drug(s) will be recorded in the subjects’ case histories. For all adverse events, sufficient information will be pursued and/or obtained so as to permit 1) an adequate determination of the outcome of the event (i.e., whether the event should be classified as a *serious adverse event*) and; 2) an assessment of the causal relationship between the adverse event and the study drug(s).

Adverse events or abnormal test findings felt to be associated with the study drug(s) will be followed until the event (or its sequelae) or the abnormal test finding resolves or stabilizes at a level acceptable to the Sponsor-Investigator.

Abnormal test findings

An abnormal test finding will be classified as an *adverse event* if one or more of the following criteria are met:

- The test finding is accompanied by clinical symptoms
- The test finding necessitates additional diagnostic evaluation(s) or medical/surgical intervention; including significant additional concomitant drug treatment or other therapy
 - Note: simply repeating a test finding, in the absence of any of the other listed criteria, does not constitute an adverse event.

- The test finding leads to a change in study drug dosing or discontinuation of subject participation in the clinical research study
- The test finding is considered an adverse event by the Sponsor-Investigator of the IND application

Causality and severity assessment

The Sponsor-Investigator of the IND application will promptly review documented adverse events and abnormal test findings to determine 1) if the abnormal test finding should be classified as an adverse event; 2) if there is a reasonable possibility that the adverse event was caused by the study drug(s); and 3) if the adverse event meets the criteria for a *serious adverse event*.

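### Section 5.2's referral for numbness beyond 72-76 h presumes an inpatient, and no contact is timed to that point for patients already discharged

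*Combined protocol and SAP*

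**What the plan says.** Section 5.2 (prolonged numbness) treats numbness outlasting mean plus 2 SD as a signal of possible nerve damage from surgery, block or other factors. It sends any such patient to Physical Medicine and Rehabilitation: "beyond 72-76 hr after injection, then the participant will be referred (presumably while still in the hospital". For minor persisting symptoms it adds that "patients will be similarly referred to the Physical Medicine and Rehabilitation Service for outpatient workup".

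Section 4.1 has outcomes evaluated "throughout the remainder of the hospital stay (which typically ranges from 2 to 5 days, including discharge day". Section 4.3 limits the daily visits: "Post-op in hospital visits will occur while the patient is in the hospital". The Crude Sensory Examination in section 4.3 compares the two sides and records whether sensation is equal, "or if one side feels less than the other, or is unable to be felt (diminished or absent". The introduction to the clinical assessments in section 4.3 says that none of them is done for safety reasons. It also says there is no protocol deviation "If physical therapy testing is not completed due to the patient preparing for discharge and/or the patient has been discharged".

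In Appendix 1 as extracted, the sensory examination is marked at baseline, on Post-Op Days 1 to 5 and at Follow-Up Visit 2, but not at Follow-Up Visit 1. Footnote d allows Follow-Up Visit 1 to be a phone call.

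Section 9.2 says "Research subjects will be routinely questioned about adverse events throughout their hospital stay and at study visits". It also says "Adverse events or abnormal test findings felt to be associated with the study drug(s) will be followed until the event (or its sequelae" resolves or stabilizes, without naming a time for the next look.

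**The concern.** The 72-76 h rule is the plan's own prompt to look for nerve damage. It works only if someone asks about numbness at about that time. For an inpatient, the daily examination does this. For a patient who has gone home, no scheduled step does, and the rule's wording suggests that this group was not considered.

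The inpatient examination before discharge would normally show numbness that later passes the trigger. That safeguard is weaker than it looks, because the plan does not class the examination as a safety procedure and excuses testing missed around discharge. The rationale for Amendment 8 reports several occasions on which the therapist found the patient gone or about to leave. At stake is how soon evaluation of a possible nerve injury begins.

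**Working it through.** **Plan's figures first.** With mean 48 h and SD 14 h, mean plus 2 SD is 48 + 28 = 76 h. The normal probability below 76 h is 97.7%, against 97.5% stated, so the trigger reproduces. The block-site nerve-damage rate is 9/1830 = 0.49%. A Wilson interval with continuity correction gives 0.240% to 0.968%, matching the stated 0.24% to 0.97%.

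**Who is home before the trigger.** Hours from injection to discharge on Post-Op Day k = 24k + discharge clock time − injection clock time. Assume injection at 07:00-12:00 and discharge at 10:00-16:00; neither is in the documents.
- Post-Op Day 2: 48 + 10 − 12 = 46 h to 48 + 16 − 7 = 57 h. All are before 72 h.
- Post-Op Day 3: 72 + 10 − 12 = 70 h to 72 + 16 − 7 = 81 h. Some are before the trigger.

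Post-Op Day 2 is taken as the earliest usual discharge, because section 5.1 places the 24 h outcome within in-hospital recovery.

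**How many.** Expected number = N × P(numbness beyond the trigger) × f, where f is the share discharged before it. The documents do not give f; 10% to 50% is assumed.

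| Basis | Past trigger, before f | Times f = 10% to 50% |
|---|---|---|
| Block-site nerve damage, 0.49% of 200 | 0.98 | 0.10 to 0.49 |
| Same, CI 0.24% to 0.97% of 200 | 0.48 to 1.94 | 0.05 to 0.97 |
| Trigger model (48, 14), beyond 76 h, of 160 | 3.6 | 0.4 to 1.8 |
| Trigger model (48, 14), beyond 72 h, of 160 | 6.9 | 0.7 to 3.5 |
| Observed block duration (40, 14), beyond 76 h, of 160 | 0.8 | 0.1 to 0.4 |
| Observed block duration (40, 14), beyond 72 h, of 160 | 1.8 | 0.2 to 0.9 |
| Theoretical numbness of 12-16 h (section 5.2) | about 0 | about 0 |

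On the trigger model the expected number passes one when f exceeds 1/3.64 = 27% (76 h) or 1/6.92 = 14% (72 h). On the block-site rate, staying under one at the upper confidence limit depends on the 50% cap: at f = 75% it is 1.94 × 0.75 = 1.46.

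The rule also covers surgical causes. Section 5.2 cites 0.2% to 8% nerve damage after hip replacement, which is 0.2 to 8 of 100 THA patients before f.

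**How late.** If Follow-Up Visit 1 falls at week 2, the next scheduled contact is 14 − 3 = 11 days after the trigger. Week 2 is an assumption: the current text fixes no week, and Amendment 6 dropped that name because the visits did not always fall then.

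**The case against.** The strongest reply is that the plan already covers these patients. Section 5.2 refers any patient with such numbness; the remark about still being in hospital is an expectation, not a condition. An outpatient route to the same service exists. Sensation is examined on each inpatient day, findings thought to be drug-related are followed to resolution, and adverse events are asked about at study visits. The manual of operating procedures, which is not among the documents, could contain a discharge call.

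Much of this stands. A reader might infer that nerve injury in discharged patients would go undetected, or that adverse events are not sought after Post-Op Day 2 because Appendix 1 as extracted marks them only that far. The documents do not support either inference: section 9.2, read here as governing, extends questioning to study visits, and the outpatient route remains open. None of these provisions is timed to 72-76 h, however, so delay remains possible.

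A reader might also infer from the 0.5% rate that fewer than one patient is affected. That is not established either. The rate counts only damage traced to the injection site, whereas the rule covers numbness from any cause. The trigger model may overstate the count, because it uses analgesia duration for numbness and section 5.2 suggests numbness of 12-16 h. But the plan calls that figure theoretical and says it has no separate data on numbness duration.

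**Conclusion.** The gap is real and minor. As written, the plan can apply its own safety rule late to patients who leave before 72-76 h. The effect is on the timing of referral; the primary outcome, sample size and main analysis are untouched.

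The number affected cannot be determined from the documents. The supportable range is from near zero to about 3.5 of 160 four-drug patients, before any allowance for surgical causes. It depends on the unstated early-discharge share and the unknown duration of numbness. The conclusion that some patients leave before the trigger also rests on the assumed clock times, but for Post-Op Day 2 discharges the margin is at least 72 − 57 = 15 h. If the manual already schedules a timed call, a cross-reference in section 5.2 settles the point.

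**What to change.** Add to section 5.2: for any patient discharged before 76 h whose last inpatient Crude Sensory Examination showed diminished or absent sensation in the block territory, or was not done, make one contact at about 76 h after injection. Use the phone, or MyHealtheVet if the patient is signed up. Record a dated yes/no on remaining numbness, and refer to Physical Medicine and Rehabilitation if yes. Ask the same patients again at Follow-Up Visit 1. The trigger value and referral pathway stay as the sponsor set them.

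The text cost is one sentence in section 5.2 and one line on the Follow-Up Visit 1 form. The workload depends on the same unknowns. On the trigger model, 26% (at 57 h) to 56% (at 46 h) of patients would still be numb at a Post-Op Day 2 discharge. With 20 to 100 of 200 discharged early, that is 20 × 0.26 = 5 to 100 × 0.56 = 56 contacts, plus any for missed examinations. Applying that model to the plain-bupivacaine arm as well makes the upper figure generous. If numbness lasts only 12-16 h, the contacts come almost entirely from missed examinations. A fair range is a few to perhaps 50-60 short coordinator contacts over the trial. The other cost is that self-report replaces examination at that point.

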
5.3 Incidental Findings.

All instances of incidental findings considered to be clinically significant will be addressed in the following manner: the PI will determine whether a finding is significant to warrant further action. If the PI determines the finding is serious enough to be labeled an adverse event; then the issue will be addressed with the patient’s primary care physician or another specialist. If the finding is not a serious event, then it will be listed as ‘incidental’ and no further action will be taken.

NOTE: The study team will capture the study data using CRFs that have been created by the study team. All hard copy documents will be protected and stored using generally-accepted measures for research confidentiality.

5.4 Interim Analysis.

During the course of a clinical trial, there is an ethical mandate to monitor the progress of the trial with interim analyses to ensure patient safety. A number of group sequential methods have been developed which permit comparisons to be made, while maintaining an overall type I error rate. The investigators will work with the Data and Safety Monitoring Board to select an interim monitoring approach. It is likely that an approach which adjusts the type I error rate in a non-uniform fashion, so that the majority of the type I error is conserved for the final treatment comparison. Thus, a large difference would be needed early in the trial to find a significant difference. Statistical significance parameters will be appropriately adjusted to account for these multiple interim analyses. At this time, the interim analyses are projected to occur (separately for TKA and for THA) at 5/20 patients and at 10/40 patients. If at these points the specific aims have been met (for the ISOC MMPNA treatment), then the Data Safety Monitoring Board will be charged with the decision to terminate the study.

5.5 Dissemination of Results.

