9.0 Adverse Event Reporting

9.1 Adverse event definitions

Adverse event means any untoward medical occurrence associated with the use of the drug in humans, whether or not considered drug related.

Adverse reaction means any adverse event caused by a drug.

Suspected adverse reaction means any adverse event for which there is a reasonable possibility that the drug caused the adverse event. Suspected adverse reaction implies a lesser degree of certainty about causality than “adverse reaction”

- *Reasonable possibility.* For the purpose of IND safety reporting, “reasonable possibility” means there is evidence to suggest a causal relationship between the drug and the adverse event.

Life-threatening, suspected adverse reaction. A suspected adverse reaction is considered “life-threatening” if, in the view of either the Investigator (i.e., the study site PI) or Sponsor, its occurrence places the patient or research subject at immediate risk of death. It does not include a suspected adverse reaction that had it occurred in a more severe form, might have caused death.

Serious, suspected adverse reaction. A suspected adverse reaction is considered “serious” if, in the view of the Investigator (i.e., the study site PI) or Sponsor, it results in any of the following outcomes: death, a

life-threatening adverse reaction, inpatient hospitalization or prolongation of existing hospitalization, a persistent or significant incapacity or substantial disruption of the ability to conduct normal life functions, or a congenital anomaly/birth defect.

- Important drug-related medical events that may not result in death, be life-threatening, or require hospitalization may be considered “serious” when, based upon appropriate medical judgment, they may jeopardize the research subject and may require medical or surgical intervention to prevent one of the outcomes listed in this definition. Examples of such medical events include allergic bronchospasm requiring intensive treatment in the emergency room or at home, blood dyscrasias or convulsions that do not result in inpatient hospitalization, or the development of drug dependency or drug abuse.

Unexpected, suspected adverse reaction. A suspected adverse reaction is considered “unexpected” if it is not listed in the general investigational plan, clinical protocol, or elsewhere in the current IND application; or is not listed at the specificity or severity that has been previously observed and/or specified.

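### Section 5.3 makes seriousness the threshold for calling an incidental finding an adverse event, contrary to 9.1 and 9.2; if 5.3 is applied, non-serious events may be missing from the 5.2 incidence

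*Combined protocol and SAP*

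**What the plan says.** Section 5.3 (Incidental Findings) states its scope as follows: "All instances of incidental findings considered to be clinically significant will be addressed in the following manner". The PI first decides whether a finding warrants further action. The next condition reads "If the PI determines the finding is serious enough to be labeled an adverse event"; where it is met, the matter is taken up with the patient's primary care physician or another specialist. The alternative begins "If the finding is not a serious event, then it will be listed as" and ends with the label incidental and no further action.

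Section 9.1 gives the general definition: "Adverse event means any untoward medical occurrence associated with the use of the drug in humans, whether or not considered drug related".

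Section 9.2 sets the recording duty, which covers "All observed or volunteered adverse events (serious or non-serious) and abnormal test findings, regardless of study group" or suspected causal relationship. It then lists four criteria, any one of which makes an abnormal test finding an adverse event. Two of them are "The test finding is accompanied by clinical symptoms" and "The test finding necessitates additional diagnostic evaluation(s) or medical/surgical intervention". The other two are a change in dosing or participation, and the Sponsor-Investigator's own view that the finding is an adverse event. The Sponsor-Investigator's review in 9.2 takes adverse event status, causality and seriousness as three separate questions.

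Section 5.2 calculates the six-week incidence of individual adverse events, with 95% confidence intervals, by organ system and relatedness in each group. It is not limited to serious events.

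**The concern.** Seriousness and adverse event status are different determinations, and 9.1 and 9.2 keep them apart. Section 5.3 runs them together: the sentence on labelling uses seriousness as the entry condition, and the following sentence repeats it in the negative. A reader who follows 5.3 literally would not label a clinically significant, non-serious finding as an adverse event. A reader who follows 9.1 and 9.2 could label the same finding as one.

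What is at stake is the numerator of the 5.2 incidence. The later safeguards also work on findings recognised as adverse events or abnormal test findings. These are the causality review in 9.2, its default of treating events of questionable relationship as associated with the study drugs, and the adverse event data that the external DSMB reviews under section 8.0. A finding closed as incidental might not reach any of them.

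**Working it through.** The plan states no figure on this point, so the check is a comparison of the sections.

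1. **Scope.** Section 5.3 covers findings already considered clinically significant, so the rule is not confined to trivial observations.
2. **Threshold.** In 5.3 the label requires the PI to judge the finding serious enough. In 9.1 there is no seriousness condition. In 9.2 each of the four criteria for an abnormal test finding is sufficient by itself, and none mentions seriousness.
3. **Order of decisions.** In 9.2, adverse event status is the first question and seriousness the third. In 5.3 the answer on seriousness settles adverse event status.
4. **Test case.** Take an abnormal test finding with clinical symptoms that is clinically significant but not serious. Under 9.2 the symptom criterion is met, so it is an adverse event and is recorded as such. Under 5.3 it is not a serious event, so it is listed as incidental. The two sections classify the same finding differently.
5. **Width of the overlap.** The four criteria apply to abnormal *test* findings; other incidental findings fall under the 9.1 definition alone. A finding on which no further action is taken would seldom meet the criterion of needing additional evaluation or intervention, so the symptom criterion is the clearest point of conflict.
6. **Precedence.** No section says that 5.3 overrides 9.2 or the reverse, and none says whether incidental entries enter the 5.2 incidence.

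**Weight of one omitted patient (illustration only).** Section 4.1 plans 20 TKA + 20 THA = 40 active control patients and 80 TKA + 80 THA = 160 MMPNA patients. Taking crude proportions at full enrolment, one affected patient left out of the numerator lowers the observed incidence by:

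- active control: 1/40 = 2.5 percentage points;
- MMPNA: 1/160 = 0.625 percentage points.

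The product-limit estimate planned in 5.2 would differ slightly with censoring. The documents give no expected number of incidental findings, so the total under-count cannot be calculated.

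**The case against.** The best defence is that 5.3 is a referral rule in loose language. It opens with whether a finding warrants further action, its consequence is a conversation with another physician, and it mentions neither case histories nor adverse event tables. On that reading its wording about seriousness is everyday usage, and 9.2, as the dedicated recording section, governs what is counted. If staff follow 9.2, nothing is lost. This is a possible reading, but 5.3 speaks expressly of labelling a finding an adverse event, sits directly after the adverse event analysis, and does not refer to section 9.

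Several stronger readings are tempting, and the documents do not support them:

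- A reader might infer that non-serious events *are* left out of the 5.2 incidence. That follows only if 5.3 is the rule applied.
- A reader might infer that mild and moderate events are missed. Seriousness is not severity: a severe event can be non-serious, and 5.3 says nothing about severity grades.
- A reader might infer that 5.3 defeats a duty to follow every event. The follow-up text in 9.2 covers only events or abnormal test findings felt to be associated with the study drugs.
- A reader might infer that every incidental finding ought to count. Some, such as pre-existing conditions, may not be adverse events under 9.1 at all.

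It is also fair to say that the effect is limited. The primary endpoint is not touched, and 5.2 places clinical judgement above statistical testing for adverse events.

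**Conclusion.** Section 5.3 is wrong as written. It sets a seriousness condition that 9.1 does not contain and that 9.2 treats as a separate question. The consequence is conditional: if 5.3 is applied, non-serious adverse events found incidentally may be missing from the 5.2 six-week incidence and from causality review. The size is unknown. Section 4.1 says that all study team members are blinded to the nerve block drug; assuming that the blind holds for the PI, the effect is mainly under-counting in both arms, with no identified bias between them. The contradiction rests on the text alone and does not depend on the illustrative figures.

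**What to change.** Amend 5.3, for recording and counting, to:

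- remove seriousness as the threshold for the adverse event label;
- classify incidental findings by the 9.1 definition and, where they are abnormal test findings, by the 9.2 criteria;
- state that findings that qualify enter the 5.2 incidence whatever their seriousness;
- keep the incidental label for findings that meet neither.

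Separately, the investigators must reconcile the statement that no further action will be taken with the 9.2 follow-up text for events or abnormal test findings felt to be associated with the study drugs. No clinical rule is proposed here.

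The cost is an amendment of a few sentences and perhaps slightly more non-serious events recorded. Design and sample size do not change.
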